1.0 Background and Study Rationale

Melanoma is an aggressive form of skin cancer with historically poor outcomes, especially prior to the advent of modern checkpoint blockade and targeted antitumor agents. Immunotherapy has changed the field of melanoma considerably in the last 5 years. In the Checkmate-066 trial, patients with metastatic melanoma who received single agent nivolumab had a 1-year overall survival of 72.9%, compared to 42.1% with the prior standard of care, dacarbazine ³. While these results are promising, only 31% patients with locally advanced or metastatic melanoma have a durable progression free survival at 4 years with the remainder progressing or relapsing ⁴. The potential mechanisms by which patients are refractory to or develop resistance to immunotherapy are numerous and include loss of the antigenic target, T-cell exhaustion, and development or enhancement of an immunosuppressive tumor microenvironment (TME) ⁵. Sensitizing these patients to immunotherapy is the focus of current drug development and ongoing clinical trials.

The phosphoinositide 3-kinase (PI3K) signaling pathway functions at many stages of cancer biology including cell division, differentiation, motility and metabolism ⁶. Inhibitors downstream of the PI3K pathway are active in some solid tumors, including everolimus in neuroendocrine tumors ⁷ and everolimus with exemestane in breast cancer ⁸. While these therapies have clinical benefit, the toxicities of inhibiting such pervasive pathways are often significant ⁹. A more targeted approach to PI3K inhibition may be useful for immune modulation in malignancies treated with immunotherapy.

PI3K has four subunits that are differentially expressed by cell type: α , β , γ and δ . While α and β are present in the majority of cell types, the PI3K γ and δ isoforms are expressed primarily in hematopoietic cells ¹⁰. Duvelisib is a potent inhibitor of both γ and δ isoforms and is FDA approved for relapsed refractory CLL/SLL and follicular lymphoma based on the DUO and DYNAMO trials ^{11,12,13}. Tumor biopsies and peripheral blood cytokine analyses from lymphoma patients treated with duvelisib demonstrated shifts to a pro-inflammatory (anti-tumor) phenotype ¹⁴.

In pre-clinical tumor models of anti-PD1 resistance, PI3K γ inhibition in combination with anti-PD1 therapy was able to restore anti-PD1 activity as demonstrated by a reduction in tumor size ¹⁵. In xenograft tumor models treated with PI3K γ inhibition, the TME demonstrated lower proportions of suppressive M2 macrophages and T-regulatory cells ¹⁵. In a mouse model of head and neck squamous cell carcinoma (HNSCC), the combination of PI3K γ inhibition and anti-PD1 blockade lead to a decrease in tumor growth and increased survival compared to mice treated with either agent alone ¹⁶. These mice were noted to have increased activation and recruitment of CD8+ T cells to tumor sites ¹⁶. Duvelisib also demonstrated anti-tumor effects in a distinct mouse model of HNSCC, with increased CD8+ T cell infiltration and less suppression by tumor-infiltrating myeloid-derived suppressor cells ¹⁷. Mice treated with both duvelisib and anti-PDL1 demonstrated increased survival and decreased rates of tumor growth compared to mice treated with anti-PDL1 alone ¹⁷.

Despite promising preclinical data, there is limited data on the use of PI3K isoform inhibitors in solid tumors. Shifts to a pro-inflammatory TME were observed in patients receiving a PI3K δ inhibitor in

combination with anti-PD1 in a phase 1b trial of patients with advanced solid tumors¹⁸. However, data regarding safety and efficacy in patients with melanoma is lacking. Taken together, these studies present duvelisib as an immunomodulator of the tumor microenvironment and a potentially effective treatment when combined with anti-PD1 therapy.

Our study will explore duvelisib as a means to overcome anti-PD1 resistance in human metastatic melanoma patients. We will test the safety and efficacy of the combination of duvelisib and nivolumab (anti-PD1) therapy in patients who have shown progression of disease on anti-PD1 therapy alone. We hypothesize that duvelisib will act as an immunomodulator, to shift the TME from an immunosuppressive to an immunostimulatory setting, helping to overcome acquired resistance in anti-PD1 treated patients. The phase I portion of our study is uniquely designed to find the ideal dose of duvelisib as an immunomodulator, which we suspect to be lower than the previously determined maximum tolerated dose (MTD) of duvelisib in lymphoma studies. In the absence of clinical dose-limiting toxicities (DLTs), immunologic parameters measured in blood and tumor samples will be used to determine dosing for the phase II portion of the study. Further, our translational correlative studies on peripheral blood and tumor biopsies will help elucidate mechanisms of resistance and the role of duvelisib in PD1 refractory settings. This is a promising area with the potential for great clinical benefit in multiple solid tumors.

2.0 Study Objectives

2.2 Primary Objectives

- Phase I:
 - To determine the maximum tolerated dose (MTD) and recommended phase II dose (RP2D) of duvelisib when combined with anti-PD1 therapy nivolumab by immunologic profiling and toxicity data.
- Phase II:
 - To assess the anti-tumor activity of the combination of duvelisib and nivolumab therapy, comparing disease change documented in CT measurements 12 weeks after initiation of therapy to baseline scans, and every 12 weeks thereafter.

2.3 Secondary Objectives

- Phase I:
 - To assess early (within 4 weeks) and late toxicities (after 4 weeks) of combination duvelisib and nivolumab
 - To assess the anti-tumor activity of the combination of duvelisib and nivolumab therapy, comparing disease change documented in CT measurements 12 weeks after initiation of therapy to baseline scans, and every 12 weeks thereafter.

- Phase II:
 - To assess the potential antitumor response of the combination of duvelisib and anti-PD1 therapy
 - To assess the duration of response with this combination
 - To assess progression-free survival and overall survival
 - To assess the safety of the combination of duvelisib and anti-PD1 therapy
 - To evaluate differences in response between certain pre-specified subsets of melanoma patients, including those who progressed on anti-PD1 therapy within 3 months (early progressors) and those who progressed after 3 months (late progressors), as well as by BRAF mutation status

2.4 Exploratory Objectives

- To evaluate how immune cell populations change by duvelisib dose, to help inform recommended phase II dosing
- To evaluate the effects of duvelisib on the tumor microenvironment (TME)
- To explore mechanism of anti-PD1 resistance and the role of duvelisib in overcoming this resistance

3.0 Investigational Plan

3.1 General Study Design

This trial is a phase I/II, dose-escalation and dose-expansion, open-label, single-arm trial in which duvelisib will be studied in combination with nivolumab.

3.1.1 Screening of Subjects

Patients will be identified during evaluation by their oncologist. Once identified, patients will meet with clinical research staff to determine eligibility, perform screening and discuss consent.

3.1.2 Study Intervention

Once consented patients should begin protocol treatment within 28 days. Treatment delays should be discussed with the Principal Investigator. If protocol is not initiated as specified, the patient's registration for the study may be cancelled.

3.1.3 Follow-Up Phase

Patients who discontinue study participation will be evaluated as determined by the treating physician regardless of the reason(s) for discontinuation (patient withdrawal, disease progression, toxicity). Patients will be followed for a minimum of 1 month after discontinuation of the study to complete data collection regarding safety. Patients may be contacted for survival follow-up for up to 5 years. Survival follow-up will be performed at approximately 3-month intervals. Patients discontinuing the study for adverse events will be followed until resolution or stabilization of the adverse event, with a minimum of 1 month follow-up.

3.1.4 Allocation to Interventional Group

The study is a single arm trial, and all patients will be allocated to the interventional group. The study coordinator at UPMC will be responsible for enrolling patients at each dose level and assigning appropriate doses.

3.2 Study Endpoints

3.2.1 Primary Endpoints

- Phase I
 - RP2D of duvelisib when used in combination with nivolumab, as determined by immunomodulatory effect in peripheral blood and TME, toxicity, and any early efficacy signals.
 - Maximum-tolerated dose of duvelisib in combination with nivolumab.

- Phase II
 - Overall response rate of the combination of anti-PD1 therapy and duvelisib as measured by overall antitumor response (defined as complete response + partial response) based on RECIST v1.1 criteria initially assessed at 12 weeks after initiation of the combination, compared to baseline imaging obtained immediately prior to initiating combination, and subsequently at 12 week intervals until progression.

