14.0 Statistical Methods

This clinical trial includes a phase I dose-finding study and a phase II efficacy study. The phase I portion requires up to 18 patients. The phase II portion needs an additional 24 patients (6 carried over from phase I using the RP2D level) for a study total of up to 42 patients and a phase II total of 30 patients. With 2 centers, each accruing 1-2 patients per month, we anticipate completing enrollment in 18 months.

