14.1. Phase I Portion of the Study

14.1.1. Study Design

The primary objectives of the phase I portion are to determine the maximum tolerated dose (MTD) of duvelisib when combined with anti-PD1 therapy nivolumab, and to decide on its recommended phase II dose (RP2D). Dose escalation will follow the decision rule in the following table, using the three dose levels defined in Section 7.5 (i.e., 15mg Daily, 25mg Daily, and 25mg BID), starting from the lowest dose. The MTD is defined to be the highest dose level at which no more than 1 of 6 treated patients experiences a DLT (DLT is defined in Section 8.1). Cohorts of three to six patients each will be treated at a dose level. Patients should have taken 75% of pills to be included in analysis of their respective cohort, as assessed through pill counts and pill diary. Only toxicities observed during the first treatment cycle will affect dose escalation. Late toxicities observed will be discussed at monthly data safety monitoring boards to determine if dose adjustments should be made.

After MTD is determined, we will decide on RP2D based on an overall consideration of DLT data, as well as immune cell profiling with laboratory correlates. For this purpose, our decision rule in the following table is a slight modification of the standard “3+3” to make sure 6 patients will be accrued at each safe dose in order to have enough patients for laboratory evaluations. RP2D should not be higher than MTD. If the MTD is not reached, RP2D will be decided based on safety data from acute and late toxicities as well as immune cell profiling data by the investigators (see section 13.1).

DECISION RULES FOR DOSE LEVEL ESCALATION

No. of patients with DLT's at this dose level	No. of patients treated at this dose level	Action
≤1	3	Treat 3 more patients at this dose level.
≤1	6	Treat 3 patients at the next higher dose level (or if at the highest level, stop the trial, and declare the dose at this level to be the MTD).

>1	3 or 6	Stop dose escalation. The previous dose is defined as MTD.
----	--------	--

Cohorts need not be completed if clear decisions can be made on the basis of an incomplete cohort. For example, if the first two patients in an intended cohort of three experience DLT's, escalation can be stopped without accruing the third member of the cohort.

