14.2.2. Study Design and Interim Analysis

The primary objective of this study is to evaluate the overall response rate to the combination of anti-PD1 therapy and duvelisib. We would consider the combination futile and not worth further study if the response rate is 5% or lower. We will monitor the efficacy of the regimen using a Bayesian method. We will consider the trial futile and propose stopping if the posterior probability that response rate is <5% given the observed data is >70%. A non-informative prior of Beta (0.5, 0.5) is used for the true response rate and the cohort size is set to be 5. The futility early stopping boundaries are given in the following table:

# Patients (inclusive)	# Responses (inclusive) are considered futile	Actions
5	Never stop with this many patients	
10	Never stop with this many patients	
15	0	Early stopping
20	0	Early stopping
25	0	Early stopping

Therefore, if none of the first 15 patients responds to the combination, the study will be stopped early for futility. Otherwise, the study will continue to recruit all 30 patients. By the end of the study, we will consider the study combination effective and worth further study if the posterior probability that the response rate is $>5\%$ given the observed data is 90% or higher (in our case, if we observe >3 responses in 30 evaluable patients). The following figure demonstrated the simulation results of the operating characteristics of our study design, under the assumption of various true response rates. As shown, when the response rate is 5% or lower, the probability of early stop is higher (>0.46) and probability of declaring efficacy (i.e. “type I error”) is low (<0.06). When the response rate is 20% or higher, the probability of early stopping is less than 3.5% and the probability of declaring efficacy (i.e. “power”) is over 86%.

The simulation is performed using the web tool for Bayesian Efficacy Monitoring Via Posterior Probability (<http://www.trialdesign.org/one-page-shell.html#BEMPO>).

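### The stated type I error below 0.06 holds only if the 6 carried-over phase I patients are not selected on response, and the plan is inconsistent on whether they may be

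*Combined protocol and SAP*

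**What the plan says.** The plan describes the RP2D decision in two ways. Section 3.2.1 (phase I primary endpoint) has it set "as determined by immunomodulatory effect in peripheral blood and TME, toxicity, and any early efficacy signals". Section 14.1.1 says instead that "we will decide on RP2D based on an overall consideration of DLT data, as well as immune cell profiling with laboratory correlates". Sections 8.1 and 13.1 also mention only toxicity and immune data. No section ranks or weights the criteria.

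Section 14.1.1 modifies the 3+3 rule "to make sure 6 patients will be accrued at each safe dose in order to have enough patients for laboratory evaluations", so up to three groups of 6 may be available when the dose is chosen. Section 14.0 then reads "The phase II portion needs an additional 24 patients (6 carried over from phase I using the RP2D level", which gives a phase II total of 30.

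Section 14.2.2 applies its futility and success rules to those 30. It says that at a true rate of 5% or lower the probability of declaring efficacy "is low (<0.06). When the response rate is 20% or higher, the probability of early stopping is less than 3.5"%. It gives no condition on how the first 6 patients came to be included, and no analysis of the 24 new patients alone.

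**The concern.** If a dose is taken forward partly because its patients responded, those responders enter the primary endpoint with it. They make up 6 of 30, or 20%, of the primary analysis set. Operating characteristics computed for 30 unselected patients would then understate the false-positive probability and overstate how often futility stopping protects patients from an inactive combination.

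The timing makes this possible. Section 13.1 places the on-treatment biopsy at 12 weeks, to coincide with the efficacy evaluation. Section 2.3 makes phase I anti-tumor activity on 12-week CT a secondary objective. Response can therefore be known when the immune data that inform the RP2D are read. With no concurrent control, the ORR rule is the trial's only guard against a false positive.

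**Working it through.** **Inputs.** All are from Section 14.2.2 unless noted.
- Null rate 5%: "We would consider the combination futile and not worth further study if the response rate is 5% or lower".
- Prior and looks: "A non-informative prior of Beta (0.5, 0.5) is used for the true response rate and the cohort size is set to be 5".
- Futility: "if none of the first 15 patients responds to the combination, the study will be stopped early for futility". The stops at 0/20 and 0/25 add nothing, because a trial that passes 15 already has a response.
- Success: at least 4 responses in 30.
- 6 carried-over plus 24 new patients (Section 14.0).
- Assumptions of this check: the 6 are counted first, and all eligible doses have the same true response rate.

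**Step 1. Reproduce the plan.** Under the Beta(0.5, 0.5) prior, Pr(ORR > 5%) is 0.890 at 3/30 and 0.968 at 4/30, so 4 is the correct cut-off for the 90% rule. At a true 5%:
- Early stop = 0.95^15 = 0.463 (stated >0.46).
- Type I error = P(≥4 of 30) − P(0 of 15) × P(≥4 of 15) = 0.0608 − 0.4633 × 0.0055 = 0.0582 (stated <0.06).

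At a true 20%, power is 0.865 (stated over 86%) and early stopping is 0.0352, which agrees with the stated 3.5% to within simulation rounding. The plan's figures are correct for 30 unselected patients.

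**Step 2. Full selection on response.** If the best-responding of m doses is chosen, the count among the 6 is the maximum of m independent Binomial(6, 0.05) counts: P(max ≤ x) = P(Bin(6, 0.05) ≤ x)^m.

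| x among the 6 | m = 1 | m = 2 | m = 3 |
|---|---|---|---|
| 0 | 0.7351 | 0.5404 | 0.3972 |
| 1 | 0.2321 | 0.3952 | 0.5077 |
| 2 | 0.0305 | 0.0600 | 0.0885 |
| 3 | 0.0021 | 0.0043 | 0.0064 |
| 4 or more | 0.0001 | 0.0002 | 0.0003 |
| Mean | 0.300 | 0.529 | 0.705 |

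Early stop = P(x = 0) × 0.95^9, with 0.95^9 = 0.6302. This gives 0.463, 0.341 and 0.250.

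Type I error = Σ P(x) × P(Bin(24, 0.05) ≥ 4 − x) − P(early stop) × 0.0055. The 24-patient tail probabilities for needing 4, 3, 2 and 1 responses are 0.0298, 0.1159, 0.3392 and 0.7080. For m = 3: 0.0118 + 0.0588 + 0.0300 + 0.0045 + 0.0003 − 0.0014 = 0.104. For m = 2 the result is 0.0836, and for m = 1 it is 0.0582 as in Step 1.

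**Step 3. Partial selection.** The plan gives no weight for efficacy. Assume the best-responding dose is chosen on response with probability w, and otherwise a dose is chosen without regard to response. Then the error is w × (full selection) + (1 − w) × 0.0582.

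| w | Two doses | Three doses |
|---|---|---|
| 0 | 0.058 | 0.058 |
| 0.25 | 0.065 | 0.070 |
| 0.50 | 0.071 | 0.081 |
| 1 | 0.084 | 0.104 |

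The bound of 0.06 is crossed at w = (0.06 − 0.05824)/(0.08361 − 0.05824) = 7% with two doses, and at (0.06 − 0.05824)/(0.10413 − 0.05824) = 4% with three.

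**Step 4. The ORR estimate.** Count a stopped trial as 0%. A trial stopped at 15 forgoes 15 × 0.05 = 0.75 expected later responses, so the mean ORR = (mean of the 6 + 24 × 0.05 − 0.75 × P(early stop))/30.
- No selection: (0.300 + 1.20 − 0.347)/30 = 3.8%.
- Best of two: (0.529 + 1.20 − 0.255)/30 = 4.9%.
- Best of three: (0.705 + 1.20 − 0.188)/30 = 5.7%.

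**The case against.** The strongest reply is that the inflation is conditional and may not occur. Efficacy comes last in the Section 3.2.1 list and carries no stated weight, and Section 14.1.1, the fullest account of the decision, leaves it out. On that reading Section 14.2.2 stands as written. Even if efficacy is an input, at a true 5% there is no responder among 18 phase I patients with probability 0.95^18 = 0.40, and response then cannot steer the choice. Fewer than three doses may also prove safe. If each level had a 20% DLT rate (an assumption), all three would be safe with probability 0.28. Averaged over the number of safe doses, given at least one, full selection would then give 0.084. All of this stands, so 0.104 is a ceiling and not an expectation.

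The objection does not remove the point. The two sections do disagree, and the stated bound has almost no slack (0.0582 against 0.06), so slight selection on response exceeds it.

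A reader might also infer that the ORR is simply biased upward, for example averaging about 6.3% at a true 5%: (0.705 + 1.20)/30. That figure ignores the planned futility stop. With the stop applied, best of two averages 4.9%, slightly below the truth, and best of three exceeds it by 0.7 points. What holds is that selection raises the estimate relative to no selection.

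**Conclusion.** The concern holds in conditional form. The type I error in Section 14.2.2 is correct arithmetic for 30 unselected patients. If at least two doses are eligible and response influences the choice beyond the small weights in Step 3, the error at a true 5% exceeds 0.06: about 0.065 to 0.081 under moderate influence, and at most 0.084 (two doses) or 0.104 (three doses). Futility stopping at 5% falls from 0.463 to as low as 0.341 or 0.250. These figures assume equal true rates across doses, and the intermediate values depend on an assumed weight that the plan does not give.

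A reader might conclude outright that the <0.06 figure is false. The documents do not support that: with one eligible dose, or a choice made without regard to response, it stands. A reader might also think that dropping efficacy from Section 3.2.1 settles the matter. It may not, because Section 13.1 describes intratumoral CD8+ proliferation, one of the immune measures meant to inform the RP2D, as correlated with anti-tumor response. This is a should-fix point. The textual conflict is certain, but the size of the effect is not.

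**What to change.** 1. Reconcile Sections 3.2.1 and 14.1.1 so that both say the same about whether efficacy informs the RP2D, and do so before phase I responses are reviewed.
2. In Section 14.2.2, state that the <0.06 figure assumes the 6 carried-over patients are not selected on response, and that the error can reach about 0.08 (two eligible doses) to 0.10 (three) if they are.
3. Whichever way item 1 is settled, pre-specify the ORR with its exact 95% confidence interval in the 24 newly enrolled patients, reported beside the 30-patient figure. This covers any selection that acts through the immune markers.

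The cost is a less favourable stated error rate and one additional, less precise ORR line. No extra patients, visits or samples are needed, and the 30-patient decision rule can stay as it is.

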3.2.2 Secondary Endpoints

Several secondary endpoints will be analyzed as follows:

- Acute and late toxicities rates throughout treatment, as graded by CTCAE v5.0 in patients at each dosing interval and in the expansion cohort
- Clinical benefit of combination therapy, defined as complete response, partial response and stable disease as assessed by RECIST v1.1, initially assessed at 12 weeks after initiation of therapy and subsequently at 12-week intervals until progression

- Duration of response defined by time at which measurement criteria are first met for complete response or partial response until the first time at which progressive disease is objectively documented
- Progression-free survival defined as time at start of treatment and first date of documented progression or death due to any cause
- Overall Survival defined as the time of start of treatment and the date of death due to any cause. Patients who are alive will be censored at the time of the last follow-up. Patients will be followed for survival for 5 years.
- Safety of the combination of anti-PD1 and duvelisib measured by adverse events graded by CTCAE v5.0. Adverse events will be captured during treatment and 100 days after discontinuing treatment. We will continuously monitor for DLTs as defined in section 8.1 that are possibly, probably or definitely related to treatment. If the adverse event rate exceeds acceptable limits, the study will be modified or discontinued.
- Subset analysis will be performed to determine how certain disease characteristics affect response to the combination, including prior time prior to progression while on anti-PD1 therapy, presence of CNS disease, radiated CNS disease and tumor BRAF mutation status.

